10 STATISTICAL CONSIDERATIONS

10.1 Study Hypotheses and Statistical Analyses

For the primary outcomes of Stage I, t- and chi-square tests will be used to test whether the treatment group experiences superior PK at Day 14 and Tolerability at Day 42, respectively. If it is determined that the assumptions of the t-test are not met by the data, non-parametric statistical tests will be employed; Fisher's exact test will be used as deemed necessary. In the unusual occurrence that the study groups are not in equipoise with respect to the measured baseline demographic, behavioral and clinical characteristics, linear and logistic regression models will be used to compare the treatment groups, adjusted for any observed differences. The same aforementioned statistics techniques will be used for the secondary outcomes of Stage I as well as the primary and secondary outcomes of Stage II.

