10.3 Study Outcomes

Stage I- Randomized Open-Label, Parallel Group

Primary Endpoints

- 1. Pharmacokinetic superiority at Day 14
 - a) Inter- and intra- patient variability: Time to attain therapeutic plasma concentrations of itraconazole (> 500 mcg/L)
 - b) Interpatient variability as calculated by co-efficient of variation

Trough (pre-morning dose) sample will be collected at Days 14 and 42. Using validated LC-MS/MS methods, blood samples will be analyzed to quantify plasma concentrations of itraconazole and hydroxyitraconazole.

Participants should arrive to the trial site having **not** taken their morning dose of study drug.

Note: site investigators are discouraged from drawing independent PK laboratories to check itraconazole levels outside of the designated timepoints (Day 14)

2. Tolerability - ability to remain on study drug at Day 42 with less than a 7-day interruption of therapy

Secondary Endpoints

- PK at day 7 plasma concentrations of itraconazole- (comparative trough, steady state plasma itraconazole concentrations of SUBA-itraconazole 65mg capsules with food to itraconazole 100mg capsules with food over 7 days)
- 2. PK at day 42 plasma concentrations of itraconazole- (comparative trough, steady state plasma itraconazole concentrations of SUBA-itraconazole 65mg capsules with food to itraconazole 100mg capsules with food over 42 days)
- 3. Efficacy: clinical outcomes (time to relief of fungal signs and symptoms) at days 14, 28, and 42
- 4. Safety- defined as: adverse events that occurred in each study arm by Day 42
- 5. Tolerability ability to remain on study drug at Days 14 & 28
- 6. Days of Hospitalization and ICU stays at Day 42
- 7. Other health economic endpoints:
 - 1. Number of unscheduled procedures (i.e., labs, scans, etc.) at Day 42
 - 2. Total number of capsules taken at Day 42
 - 3. SF-20 (QOL) assessments at Day 42

Stage II- Open-Label, Extension

Primary Endpoint

- 1. Efficacy- Free from proven or probable invasive endemic fungal infection at Day 180
- 2. Tolerability- ability to stay on study drugs at Days 43 180.

Secondary Endpoints

- 1. Safety- Adverse events that occurred in each study arm between Days 43 180 or end of therapy
- 2. Days of Hospitalization (Days 1 180) defined as days of hospitalization and ICU stays from randomization to Day 180 or end of therapy)

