10.4 Data Review Committee

In addition to discrete laboratory parameters for PK, laboratory reports, days of hospitalization, ER and ICU stays, and safety reports; a data review committee (DRC) consisting of a DRC chair and 3 additional mycology experts will review data to determine safety and efficacy parameters as follows:

DRC-Assessments of Clinical Response (Baseline, Days 14, 28, 42, 84, 180)

| Outcome | DRC-Assessed Clinical Response |
|----------------|---|
| Success | Resolution of all attributable clinical symptoms, physical findings and radiography Partial resolution of attributable clinical symptoms, physical findings and/or radiography |
| Failure | No resolution and/or worsening of attributable clinical symptoms, physical findings, and/or radiography |
| Not applicable | No attributable signs and symptoms present at baseline and no symptoms attributable to IFD developed post-baseline |

DRC-Assessments of Mycological Response (Days Baseline, Days 14, 28, 42, 84, 180)

| Outcome | DRC-Assessed Mycological Response |
|----------------|---|
| Success | Eradication |
| | Presumed eradication |
| Failure | Persistence |
| | Presumed persistence |
| Not applicable | No mycological evidence available at baseline |

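### Stage I efficacy is worded as a time to relief, but Section 10.1 names no method for censored times and gives no rule for unrelieved patients or early leavers

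*Combined protocol and SAP*

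**What the plan says.** Section 10.3 lists Stage I secondary endpoint 3 as "Efficacy: clinical outcomes (time to relief of fungal signs and symptoms) at days 14, 28, and 42".

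Section 10.1 sets the methods. For the Stage I primaries, "t- and chi-square tests will be used to test whether the treatment group experiences superior PK at Day 14 and Tolerability at Day 42", the first test for PK and the second for tolerability. If t-test assumptions fail, "non-parametric statistical tests will be employed; Fisher's exact test will be used as deemed necessary". If the arms differ at baseline, "linear and logistic regression models will be used to compare the treatment groups, adjusted for any observed differences". It then adds: "The same aforementioned statistics techniques will be used for the secondary outcomes of Stage I". No Kaplan-Meier, log-rank, Cox or interval-censored method appears anywhere, and there is no censoring rule or missing-data rule.

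The plan nevertheless expects patients with no relief time. Section 10.4 defines clinical failure as "No resolution and/or worsening of attributable clinical symptoms, physical findings, and/or radiography". Section 5.3.2 allows discontinuation for adverse events, withdrawn consent or loss to follow-up, and Section 5.3.3 ends assessments for anyone who withdraws from the study itself.

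**The concern.** Relief is read only at visits, so each relief time is known only to an interval between visits. A patient unrelieved at Day 42, or at the last visit before leaving, has no relief time at all. A t-test needs a number for every patient it includes, and the plan does not say what number these patients get. Someone must choose after enrolment, in an open-label trial where treatment is known and dropout may differ between arms.

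The possible choices behave very differently. Analysing relieved patients only compares successes with successes. Entering the last follow-up day makes leaving look like early relief: a patient who was unrelieved at Day 14 and then left is recorded as relieved on Day 14. This is the only efficacy endpoint in Stage I, so the missing rule could decide what the trial reports about early efficacy.

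**Working it through.** **The plan's own figure.** Section 10.2 gives 77% power for the PK means (difference 60.0, SDs 94.0 and 101.8, two-sided alpha 0.05, 80 patients). With 40 per arm (assumed, as no allocation ratio is stated), the standard error is √(94.0²/40 + 101.8²/40) = √479.98 = 21.91, and 60.0/21.91 = 2.74. The unequal-variance t-test on 77.5 degrees of freedom then has 77.2% power. The figure reproduces, but it says nothing about time to relief.

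**Assumptions for relief.** The documents give no relief or dropout rates. Take exponential relief times with medians of 20 and 40 days, 40 patients per arm, visits at Days 14, 28 and 42, and no dropout. The share still unrelieved at day t is 2^(−t/median).

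| | Median 20 days | Median 40 days |
|---|---|---|
| First relieved at Day 14 | 0.384 | 0.215 |
| First relieved at Day 28 | 0.237 | 0.169 |
| First relieved at Day 42 | 0.146 | 0.133 |
| Relieved by Day 42 | 0.767 | 0.517 |
| No relief time | 0.233 | 0.483 |

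**t-test on relieved patients only.**
- Mean visit time: (14×0.384 + 28×0.237 + 42×0.146)/0.767 = 23.6 days, and by the same formula 25.8 days in the slower arm. A twofold difference in medians shrinks to about 2.1 days.
- The SDs of these visit times are 10.8 and 11.3. The expected numbers relieved are 40×0.767 = 30.7 and 40×0.517 = 20.7.
- Standard error: √(10.8²/30.7 + 11.3²/20.7) ≈ 3.15, so the ratio is 2.1/3.15 ≈ 0.67.
- Approximate power: Φ(0.67 − 1.96) + Φ(−0.67 − 1.96) ≈ 0.10.

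**Chi-square at Day 42.**
- Difference: 0.767 − 0.517 = 0.250. Pooled proportion: 0.642.
- Standard error: 0.107 under no difference and 0.104 under the assumed difference.
- Approximate power: Φ((0.250 − 1.96×0.107)/0.104) = Φ(0.38) ≈ 0.65.

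**Simulation** (2,000 to 4,000 trials per scenario). Dropout is generated independently of relief.

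| Handling | Power, medians 20 vs 40 days, no dropout | False positives, no true difference, dropout 5% vs 25% |
|---|---|---|
| t-test, relieved patients only | 10% | – |
| t-test, last follow-up day entered as relief | 56% | 24% |
| Chi-square at Day 42, leavers = failures | 66% | 11% |
| Chi-square at Day 42, leavers excluded | 66% (no leavers) | 5-6% |
| Log-rank at visits | 70% | 5% |

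With the common median varied from 20 to 40 days, the false-positive rates are about 19-26% (t-test on last follow-up day), 10-12% (chi-square, leavers as failures) and 5-6% (log-rank).

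**Second set of assumptions** (50% or 70% relieved by Day 42 in the comparator arm).
- Hazard ratio 2, equal dropout of 0-20%: power is 63-77% for log-rank and 8-21% for the relieved-only t-test.
- Same hazard ratio, no dropout: chi-square has 64% against 68% for log-rank at 50% relief, and 67% against 77% at 70% relief.
- No true difference, dropout 5% vs 30%: false positives are 31-42% (t-test on last follow-up day), 13-18% (chi-square, leavers as failures), 5-7% (chi-square, unrelieved leavers excluded) and 5.4-5.7% (log-rank).

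**The case against.** The strongest reply is that the endpoint was never meant as a survival outcome. It is tied to Days 14, 28 and 42, and Section 10.4 supplies a success/failure classification on those days ("DRC-Assessments of Clinical Response (Baseline, Days 14, 28, 42, 84, 180"). On that reading an unrelieved patient is a failure and chi-square fits. This stands as a workable reading. It means the endpoint is misnamed, and a rule for leavers is still missing.

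A second reply is that the non-parametric fallback is unnamed and log-rank is itself non-parametric. A rank test giving unrelieved patients the worst rank also copes: 65% power against 69% for log-rank in a further run at the same medians. With dropout of 5% vs 25% and no true difference, it gives 5.6% false positives if unrelieved leavers are excluded and 7.9% if they are ranked worst. But the fallback applies only when t-test assumptions fail, and the plan specifies neither the test nor the ranking.

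Third, the 10% and 24% figures come from handling rules that the plan does not state. That is correct. They show what a t-test would require, not what the sponsor has said it will do. Log-rank's 5% also holds because dropout was simulated as unrelated to relief. If patients leave because of their symptoms, censoring them is biased too.

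A reader might infer two stronger points. One is that none of the listed tests can handle unrelieved patients; the chi-square results contradict that. The other is that the same fault affects primary endpoint 1(a), "Time to attain therapeutic plasma concentrations of itraconazole (> 500 mcg/L". That extension is weak. The endpoint sits under a Day 14 heading, and Appendix A schedules PK at Days 7, 14 and 42, so there are at most two readings by then. After Day 14, Section 6.3 allows dose changes prompted by the measured level, which confounds later attainment.

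**Conclusion.** The point holds in limited form. A t-test on time to relief is wrong as written, because some patients will have no relief time and no rule covers them. A chi-square at a visit is usable. It loses about 4 points of power at the assumed medians (up to about 9 in the other scenarios without dropout, 76.6% − 67.4%) and ignores timing. Its false-positive rate under unequal dropout depends on a leaver rule that the plan does not contain. The simulated rates show direction and rough size only, since they rest on assumed relief times, assumed dropout and equal arms. This is a secondary endpoint: neither the sample size nor the primary analyses depend on it. It should be corrected before outcome data are examined.

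**What to change.** Amend Section 10.1 to give this endpoint its own analysis:

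- **Event:** the first scheduled visit with DRC clinical response under Section 10.4. State whether partial resolution counts as relief, since Section 10.4 places it under success.
- **Population:** exclude the not-applicable patients, who had no attributable signs or symptoms at baseline.
- **Censoring:** patients without relief are censored at their last assessed visit.
- **Analysis:** visit-based Kaplan-Meier curves with a log-rank test or discrete-time hazard model, stratified by HIV status to match the randomisation in Section 5.3.1. Report the proportions relieved at Days 14, 28 and 42 from the same curves.
- **Sensitivity:** repeat with leavers counted as not relieved through Day 42, because censoring assumes that dropout is unrelated to symptoms. Read this as a stress test, since that rule itself inflates error when dropout is unequal.

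If the sponsor meant visit proportions, the alternative is to rename the endpoint accordingly, keep chi-square, and state the leaver rule. Either way the cost is analysis wording only: no new data, visits or patients. Leave primary 1(a) out of this change.

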5 STUDY ENROLLMENT AND WITHDRAWAL

5.1 Subject Inclusion Criteria

Subjects must meet all the inclusion criteria in order to be eligible to participate in the study as listed below:

- 1. Male and female patients age > 18 years who have given written informed consent to participate.
- 2. Patients who are unresponsive, critically ill, or requiring sedation so they are cognitively impaired will be considered unable to consent for themselves. A Legally Authorized Representative (LAR) will be approached for informed consent. LAR will be determined using this order: (a) legally appointed guardian, (b) health care proxy or authorized individual to make medical decisions in conjunction with a durable power of attorney, (c) spouse, (d) adult child, (e) parent, or (f) next of kin. Qualification of the LAR will be obtained through verbal assurance from the LAR.
- 3. Patients with a proven or probable endemic mycosis (*Histoplasma*, *Coccidioides*, *Paracoccidioides*, *Blastomyces*, *Sporothrix*, *Talaromyces marneffei* (formerly *Penicillium marneffei*) according to current EORTC/MSG criteria, including patients who:
 - Are immunosuppressed, including as a result of HIV/AIDS
 - Have had a heart, lung or bone marrow transplant
 - Have had chemotherapy for cancer
 - Are otherwise normal hosts

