6.2 Dosage, Preparation and Administration of Study Intervention/Investigational Product

Study participants will be randomized to receive either open-label SUBA-Itraconazole or conventional itraconazole. Each treatment arm will be dosed as follows:

Arm A: Open-Label SUBA-itraconazole 65 mg Capsules – administered with food

Stage 1

- Day 1 3: two 65 mg capsules, three times daily
- Day 4 42: two 65 mg capsules, twice daily

Stage 2:

Day 43 – 180: two 65 mg capsules, twice daily.

Arm B: Conventional Itraconazole 100 mg Capsules – administered with food Stage 1:

- Day 1 3: two 100 mg capsules, three times daily
- Day 4 42: two 100 mg capsules, twice daily

Stage 2:

Day 43 – 180: two 100 mg capsules, twice daily).

Based on standard of care for invasive endemic fungal infection, some participants will be prescribed conventional itraconazole (non-study drug) after Day 180 for up to a year or beyond, as prescribed by their physician. Information for discounted itraconazole will be provided at the end of the study to help defray costs.

[figure not shown]

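### Hospital and ICU days are raw counts that death cuts short, and the Days 1–180 version also stops counting at end of therapy

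*Combined protocol and SAP*

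**What the plan says.** Section 10.3 lists "Days of Hospitalization and ICU stays at Day 42" as Stage I secondary endpoint 6. The Stage II counterpart, secondary endpoint 2, is defined as "days of hospitalization and ICU stays from randomization to Day 180 or end of therapy". On analysis, Section 10.1 says "The same aforementioned statistics techniques will be used for the secondary outcomes of Stage I" and extends this to Stage II. That means a t-test or a non-parametric test, with regression adjustment if the arms differ at baseline.

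No section says how a death, or a patient who leaves the study, enters either count. Section 5.3.2 does not name death among the reasons for withdrawal.

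Four other places matter:
- Section 5.3.3 separates stopping drug from leaving the study. A patient who only stops drug stays in the visit schedule if he or she agrees.
- Appendix A collects hospital and ICU days at every visit from Day 1 to Day 180.
- Section 5.1, item 2, provides for representative consent: "Patients who are unresponsive, critically ill, or requiring sedation so they are cognitively impaired will be considered unable to consent for themselves".
- Section 5.2 excludes patients who cannot take oral medication (item 4) and those not expected to live 30 days (item 15).

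**The concern.** Fewer hospital days is naturally read as the better result. A raw count keeps that meaning only if every patient is at risk of hospital days for the whole window. Death ends that risk, so the worst outcome can give one of the lower scores. If one arm had more early in-hospital deaths, the comparison could show that arm as using less hospital care.

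The Stage II definition adds a second truncation. A patient who stops drug for toxicity or failure and is then admitted contributes none of those later days. These admissions are among the most informative about treatment, and the schedule records them for patients who stay in follow-up. At stake is the direction of a secondary resource-use comparison in a trial whose stated purpose (Section 3.1) includes cost-effectiveness.

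**Working it through.** **The plan's own figure.** The documents give no rate, SD or power for hospital days. The only computed figure is 77% power for the PK comparison (Section 10.2). With a difference of 60.0, SDs of 94.0 and 101.8, and 40 per arm (equal allocation assumed), the standard error is √((94.0² + 101.8²)/40) = 21.9. The unequal-variance t-test at two-sided 0.05 then has 77.2% power. The figure reproduces, and this point does not affect it.

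**Death, simplest case.** Assumed: 40 per arm; 3 patients in one arm die in hospital on Day 5 who would otherwise have gone home after 12 days.
- Raw hospital days: mean falls by 3 × (12 − 5)/40 = 0.525, an apparent benefit.
- Days alive and out of hospital to Day 42: each survivor would have 42 − 12 = 30 and each death has 0, so the mean falls by 3 × 30/40 = 2.25, a loss.

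**Death, a range.** Assumed: 40 per arm; 10 per arm in hospital from Day 1; survivors stay 14 days; all deaths are in arm A and in hospital. With no deaths, arm B's raw mean is 10 × 14/40 = 3.50, and its days alive and out of hospital are (10 × 28 + 30 × 42)/40 = 38.5.

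| Deaths in A | Day of death | Raw hospital days, A (B = 3.50) | Days alive and out of hospital, A (B = 38.5) |
|---|---|---|---|
| 1 | 5 | 3.275 | 37.8 |
| 1 | 10 | 3.40 | 37.8 |
| 2 | 5 | 3.05 | 37.1 |
| 2 | 10 | 3.30 | 37.1 |
| 4 | 5 | 2.60 | 35.7 |
| 4 | 10 | 3.10 | 35.7 |

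In every row arm A looks better on the raw count, by 0.10 to 0.90 days, and worse on days alive and out of hospital, by 0.7 to 2.8 days.

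**Dividing by days alive does not help.** With 4 deaths on Day 5, arm A has 104 hospital days over 4 × 5 + 36 × 42 = 1,532 days alive, or 6.79 per 100. Arm B has 140 over 1,680, or 8.33 per 100. The ordering is still reversed; the measure must count death as unfavourable.

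**When the reversal disappears.** In that same row arm A is 0.90 × 40 = 36 hospital days below arm B. If its 6 surviving inpatients each stayed 36/6 = 6 days longer (20 rather than 14), the raw means would be equal at 3.50. Days alive and out of hospital would then be (6 × 22 + 30 × 42)/40 = 34.8 in arm A. So the raw count does not always favour the worse arm.

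**Stage II cut-off.** Assumed: a patient stops drug on Day 10, stays in follow-up, and is in hospital on Days 20 to 29. The Stage I count to Day 42 is 10. The Days 1–180 count, cut at end of therapy, is 0, although its window contains the Stage I window. If 4 of 40 patients in an arm followed this pattern, 4 × 10/40 = 1.0 day would drop out of the arm mean.

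**The case against.** The strongest case against is that early deaths should be few. Section 5.2 excludes patients not expected to live 30 days and those who cannot take oral drug. Three extra Day 5 deaths among 40 is a 7.5-point excess, which is extreme for this population, and even that moves the raw mean by about half a day. A worse arm may also have longer or more admissions, which pushes the count the other way. Adverse events, tolerability and clinical response are compared separately, so excess deaths would not go unseen. All of this stands. It limits the size and certainty of the effect, but does not supply the missing rule for death. The exclusions lower the chance of early death without removing it, and Section 5.1 still foresees critically ill patients.

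For Stage II, end of therapy could be meant as the scheduled final visit. But the definition names Day 180 separately, and the Protocol Summary lets treatment end earlier when the investigator judges that safe. The cut-off therefore most naturally means the last day of drug.

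Two stronger readings are tempting and are not supported:
- A reader might infer that stopping drug also shortens the Stage I hospital count. It does not. Endpoint 6 has no end-of-therapy limit, Section 5.3.3 keeps willing patients in follow-up, and Appendix A keeps recording hospital days. The count is lost only if the patient also leaves the study.
- A reader might infer the same fault in "Total number of capsules taken at Day 42", listed under "Other health economic endpoints". The plan does not say that fewer capsules is better. Capsules not taken are truly not consumed, so the total is a valid resource input, and early stopping is already a failure on primary tolerability. Dose changes allowed by Section 6.3 can also move the total in either direction. Rescaling to a percentage of the Section 6.2 plan, 3 × 6 + 39 × 4 = 174 in both arms, divides by a constant and leaves every test unchanged.

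**Conclusion.** The point holds for hospital and ICU days only. Endpoint 6 lets an in-hospital death score as lower use than a recovery with a longer stay, and the Stage II version also discards admissions after drug is stopped. In the assumed scenarios the raw comparison is shifted by 0.10 to 0.90 days in favour of the arm with the deaths, while days alive and out of hospital differ by 0.7 to 2.8 days against it.

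These sizes rest on assumed deaths, lengths of stay and equal arms of 40; the documents give no death or hospitalisation rate. The effect is probably small and its direction uncertain. A reader might go further and infer that the resource comparison will mislead, or that harm would be hidden. The documents do not support that: misdirection is possible, not established, and the harms are reported elsewhere. Primary endpoints and power are untouched. This is a cheap improvement to secondary endpoints, not a threat to the trial.

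**What to change.** In Section 10.3:
1. Analyse days alive and out of hospital from randomization to Day 42 (Stage I) and to Day 180 (Stage II), scoring days after death as zero and counting whatever the treatment status. The tests in Section 10.1 can stay.
2. Delete the end-of-therapy limit from the Stage II hospital-day definition.
3. Show hospital days, ICU days and deaths as components, by arm.
4. Report how many patients left the study before each time point, by arm, and state in advance how their missing days are handled.

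The cost is wording. Hospital and ICU days are already on every visit in Appendix A, and deaths are captured as serious adverse events (Section 8.4.2). The exception is patients who leave the study, whose assessments stop under Section 5.3.3; item 4 is there for them. The downside is that a day dead weighs the same as a day in hospital, which the components in item 3 let the reader see through.

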3.2.2 Primary and Secondary Outcome Measures - Stage II (Open-Label Extension)

Primary Outcomes

- Efficacy by Day 180
- Tolerability by Day 180

Secondary Outcomes

- Safety by 180
- QOL (including hospital/ICU visits) Assessments by Day 180

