7.3 Follow-up

Participants will be assessed in clinic at Day 7, Day 14, Day 28 (1 month), Day 42, Day 84 (3 months) and Day 180 (6 months). In the opinion of the investigator, clinic visits may be replaced with telemedicine visits or home visits, with allowances made for blood draws at remote or commercial laboratories. Documentation in source documents should clearly define accommodations in visit locations or methods when attempting to protect participants and other patients from potential exposure and hazards related to COVID-19. The Day 7, 14 and 42 visits allow a narrow window (+/- 3 days) so that accurate PK levels can be drawn.

The Day 84 and 180 visits will allow a window of (+/- 7 days).

At each visit, blood samples will be drawn for study-specific safety and efficacy labs. In addition a quality of life questionnaire will be administered at Day 42. See Appendix A for study procedures per visit.

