7.4 Final Study Visit or Early Termination Visit

The final study visit will occur at Day 180 (with a window of +/-7 days). During this visit, a physical examination, vital signs, quality of life questionnaire, assessments of concomitant medications and adverse events and mycological assessments will take place. Blood and urine samples will be drawn for study-specific safety and efficacy labs. See Appendix A for study procedures per visit.

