8.3 Quality of Life (QOL) Evaluations

8.3.1 Short Form 12 Version 2 (SF-12v2)

The SF-12v2 is a 12-question multipurpose survey instrument derived from the larger, SF-36 [17]. The SF-12v2 has been used in numerous healthcare settings and disease types to help determine the patient's overall state of wellbeing and health-related QOL by means of assessing both physical and mental status at the time of the survey. The 8 domains of the survey are: physical functioning (PF), role-physical (RP), bodily pain (BP), general health (GH), vitality (VT), social functioning (SF), role-emotional (RE), and mental health (MH). Subjects will be administered the SF-12PK at Day 1, Day 42, and Day 180. Version 2 of the SF-12 (Optum) will be used for this study.

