APPENDIX A: SCHEDULE OF EVENTS

| Activities | Day 1 ^g (Baseline) | Day 7 (1 wk) +/- 3 days | Day 14 (2 wks) +/- 3 days | Day 28 (4wks) +/- 7 days | Day 42 (6 wks) +/- 3 days | Day 84 (3 mos) +/- 7 days | Day 180 (6 mos) +/- 7 days |
|---|----------------------------------|----------------------------------|------------------------------------|-----------------------------------|------------------------------------|------------------------------------|-------------------------------------|
| Informed Consent | Х | | | | | | |
| Review of Inclusion/Exclusion Criteria | × | | | | | | |
| Randomization | X | | | | | | |
| Medical History | X | | | | | | |
| Clinical Assessment: vital signs, PE ^a , & radiographs ^b ; | × | Х | Х | Х | Х | Х | × |
| Participant Administered SF-12 Quality of Life Survey | Х | | | | Х | | х |
| Tolerability | Х | | | Х | Х | | Х |
| βHCG - pregnancy test ^c | Х | | | | | | |
| Mycologic Assessment: clinical, urine and serum quantitative antigen levels^d & serum antibodies ^{e,f} | х | | х | Х | Х | Х | х |
| Serum and Urine for future use: blood, urine, saliva, sputume | X | | Х | X | Х | Х | Х |
| Plasma PK ^f | | Χ | Х | | Х | | |
| Chemistry: Creatinine, AST and Alkaline Phosphatase, Total Bilirubin ^f | Х | | Х | Х | Х | Х | х |
| Hematology: CBC with Differential ^f | X | | | X | | X | X |
| HIV Status: Documentation of any positive test; Documentation of Negative test 30 days or less prior to start of study drug. | Х | | | | | | |
| Antifungal Therapy (Pre- and during study) | Х | Х | Х | Х | Х | Х | Х |
| Dose Modifications | | | Х | X | Х | Х | |
| Study Drug Dosing & Accountability | Х | Х | Х | Х | Х | Х | Х |
| Concomitant Therapy | Х | Х | Х | Х | Х | Х | Х |
| Adverse Events | Х | Х | Х | Х | Х | Х | Х |
| Days of Hospitalization, ICU | Х | Х | Х | Х | Х | Х | Х |

^a Complete physical exam on baseline; targeted physical exams for all other visits.

b Radiograph results that were performed as standard of care to diagnose or assess the fungal infection.

^C Urine or Serum pregnancy test is acceptable.

^d Histoplasma and Coccidioides urine and serum quantitative antigen.

^e Collection of sputum, if associated with the IFI and available.

^fChemistry and hematology will be processed at the site for safety evaluations; PK samples will be sent to a central lab for processing; see Manual of Procedures for specimen handling procedures;

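### The Stage I QOL endpoint names the SF-20 although only the SF-12v2 is given, the Day 180 questionnaire is not listed as an endpoint, and use of the Day 1 score is left to chance imbalance

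*Combined protocol and SAP*

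**What the plan says.** The endpoint list in 10.3 places "SF-20 (QOL) assessments at Day 42" among the other health economic endpoints (Stage I secondary endpoint 7). The SF-20 appears nowhere else.

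The procedures describe a different instrument. Section 8.3.1 states "Version 2 of the SF-12 (Optum) will be used for this study". The sentence before it misprints the name: "Subjects will be administered the SF-12PK at Day 1, Day 42, and Day 180". Appendix A has one row for the instrument, "Participant Administered SF-12 Quality of Life Survey", marked at baseline, Day 42 and Day 180. The visit text in 7.3 and 7.4 agrees on the two follow-up days without naming the questionnaire: "In addition a quality of life questionnaire will be administered at Day 42" and, for the final visit, "a physical examination, vital signs, quality of life questionnaire".

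For Stage II, section 3.2.2 lists "QOL (including hospital/ICU visits) Assessments by Day 180" as a secondary outcome, and the protocol summary does the same. The Stage II secondary endpoints in 10.3 are adverse events and days of hospitalization and ICU stay.

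On analysis, 10.1 says "The same aforementioned statistics techniques will be used for the secondary outcomes of Stage I" and extends this to Stage II. Those techniques are t- and chi-square tests, with non-parametric or exact tests as needed. Regression is used only if the arms turn out to differ on measured baseline characteristics.

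**The concern.** Three gaps meet in one endpoint. The instrument named in 10.3 is not the one patients complete. The Day 180 questionnaire is promised and collected, but the section that defines endpoints does not mention it. The Day 1 questionnaire is collected, yet nothing guarantees that it enters the analysis: 10.1 makes adjustment depend on imbalance seen in the data, gives no rule for declaring imbalance, and does not mention baseline QOL.

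A fourth gap sits beneath these. Section 8.3.1 describes eight domains and refers to physical and mental status, but no section says which score is compared. In an open-label trial with a patient-reported outcome, the choices of score and adjustment should be fixed before the data are seen. Section 5.1 admits patients with HIV/AIDS, transplant or chemotherapy as well as normal hosts, so wide differences in QOL at entry are plausible, although the documents give no figure for them.

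**Working it through.** **Documents side by side**

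| Item | 10.3 | 8.3.1 and Appendix A | 3.2.1 and 3.2.2 |
|---|---|---|---|
| Instrument | SF-20 | SF-12v2 (SF-12PK in one sentence) | not named |
| Day 1 | not mentioned | collected | not mentioned |
| Day 42 | endpoint | collected | secondary outcome |
| Day 180 questionnaire | not listed | collected | secondary outcome |
| Day 180 hospital/ICU | listed | collected (Appendix A) | secondary outcome |

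The SF-20 is named once and given at no visit. The SF-12 is given at three visits, of which 10.3 uses one.

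**The plan's own figures**

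There is no QOL standard deviation, effect size or power to reproduce. The only computed figure is the 77% power in 10.2 for the pharmacokinetic comparison. It reproduces at 77.2% (unequal-variance t-test, 40 per arm, difference 60.0, standard deviations 94.0 and 101.8) and has no bearing on QOL.

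**What adjustment for Day 1 would gain**

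Inputs:
- Total of 80 patients (10.2).
- 40 per arm and no dropout: assumptions, since the protocol states neither the allocation ratio nor a dropout rate.
- Correlation r between Day 1 and Day 42 scores: assumed 0.3 to 0.7.
- Two-sided 5% level and 80% power, normal approximation, for illustration.

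Formulas:
- Share of residual variance removed = r².
- Share remaining = 1 − r².
- Equivalent unadjusted sample size = 80 / (1 − r²).
- Detectable difference in SD units = (1.960 + 0.842) × √(2/40) × √(1 − r²).

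Without adjustment the detectable difference is 2.802 × 0.2236 = 0.63 SD. With adjustment:

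| r | Removed | Remaining | Equivalent N | Detectable difference |
|---|---|---|---|---|
| 0.3 | 9% | 0.91 | 80/0.91 = 88 | 0.60 SD |
| 0.5 | 25% | 0.75 | 80/0.75 = 107 | 0.54 SD |
| 0.7 | 49% | 0.51 | 80/0.51 = 157 | 0.45 SD |

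**The case against.** A reader might infer that the planned QOL results cannot be produced at all. The documents do not support that. Section 8.3.1 states which instrument is used, Appendix A schedules it three times, 3.2.1 and 3.2.2 make QOL an outcome by Day 42 and by Day 180, and 10.1 supplies generic tests for both stages. Only a literal SF-20 score is impossible; otherwise this is a naming error with the data behind it intact.

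A reader might also infer that Day 180 QOL is missing altogether. It is not: 3.2.2 counts hospital and ICU use as part of QOL, and 10.3 lists that part. Only the questionnaire is absent, and only from the endpoint list.

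Nor does the text exclude the Day 1 score. It does not say whether the Day 42 value or the change from Day 1 is analysed, and the conditional regression in 10.1 could take in baseline QOL. The accurate criticism is that its use is not assured.

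Two further objections stand in part. An unadjusted comparison is valid under randomization, so routine adjustment is a gain in efficiency and not the removal of a bias. And Day 1 scores may be incomplete: 5.1 allows patients who cannot consent for themselves to enter through a representative, while Appendix A has the participant complete the survey. This reduces the gain and means that a missing-baseline rule is needed.

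What the objections leave untouched is the contradiction between sections, the unlisted Day 180 questionnaire, the unnamed score, and an adjustment rule that depends on the data.

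**Conclusion.** The point holds as an inconsistency in a secondary endpoint together with an avoidable loss of precision. The SF-20 and SF-12v2 texts must be reconciled, and the Day 180 questionnaire needs an entry in 10.3. These are mainly consistency corrections. The substantive improvement is to replace adjustment triggered by observed imbalance with prespecified adjustment for a score that is already scheduled.

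The gain is 9% to 49% of the residual variance over the assumed range of r, or 25% at r = 0.5. It rests on that assumed correlation, equal allocation, complete data, and a Day 1 score recorded before the allocation can influence it. Appendix A puts randomization and the survey on the same day without stating an order. The correlation with Day 180 may differ from that with Day 42, so the gain there could be smaller. Nothing here touches the primary endpoints or the sample size.

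**What to change.** 1. In 10.3, replace "SF-20 (QOL) assessments at Day 42" with: *SF-12v2 physical and mental component scores at Day 42, compared between arms by linear regression adjusted for the Day 1 score.*
2. In 10.3, add to the Stage II secondary endpoints: *SF-12v2 physical and mental component scores at Day 180, analysed in the same way.*
3. In 10.1, add: *For the SF-12v2 scores, adjustment for the Day 1 score is prespecified and does not depend on observed baseline imbalance. A missing Day 1 score is replaced by the mean of the observed Day 1 scores, and an indicator for missingness is added to the model.* Another simple rule would serve if stated in advance.
4. In 8.3.1, correct SF-12PK to SF-12v2.

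The two component scores are a reasonable choice, not one the documents dictate. If the sponsor prefers particular domains, they should be named in the same place before analysis. The cost is wording in three sections; no visit, questionnaire or patient is added, because all three administrations are already scheduled.
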